each scale usage. After demonstration, Investigator 2 will record the three dependent variables measurements on the same patients twice, with at least 48hour interval between measurements. A minimum of five patients will be used. The intra-rater reliability of measurements on the two separate days will be calculated.

Study Sequence

Investigator 1 will conduct patients' screening (Appendix F) before they enroll the study to determine their eligibility. Participants with mild cognitive impairment (MMSE 19-23) demonstrating understanding of the research and the consent decision and indicating a willingness to take part will be asked to sign a consent form. For participants with moderate cognitive impairment (MMSE 10-18), both the potential participants and their legally authorized representatives will be asked to give consent to allow study participation.

Patients will be randomly assigned using block randomization with a 1:1 allocation ratio and randomly permuted block sizes of 2 to 6 based on severity of cognitive impairment. The randomization will be performed in R software (version 4.1.2, R Core Team) using the randomize R package (version 2.0). Each subject will be randomized to one of two interventions: (1) Control group, which will receive standard physical therapy care without LSQ use; and (2) Experimental group, where physical therapists will use the LSQ. The randomization file will be generated by Investigator 1 (Physical therapist) not involved in the data collection process, with the results stored in a spreadsheet accessible only to the investigator responsible for the subjects' group assignment. This investigator will

not participate in any data collection. Due to the nature of the study, participants will not be blinded to the group assignment and to the treatment they will receive. Investigator 2 measuring the dependent variables, however, will be blinded to the group assignment.

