Family members of each patient will receive an LSQ to complete prior to the start of the intervention (Appendix A). Investigator 1 will conduct all physical therapy sessions for the study patients. Investigator 2, will collect the following dependent variables on day 1 of week 1, and on day 1 of third and sixth weeks:(1) Pittsburg Rehabilitation Participation Scale, which measures patients' participation in therapy; (2) Quality of Life - Alzheimer's disease scale; and (3) depression symptoms (Cornell Scale for Depression in Dementia). Additionally, Investigator 2 will record quality of life and depression at six-week following the intervention. Both investigators will enter their data using Texas Tech University Health Sciences Center password protected Qualtrics platform.

Both control and intervention groups will receive individual exercises that include strengthening, balance, gait, aerobic, endurance, dual cognitive motor tasks and exercises to improve activities of daily living and functional mobility²⁸. A pragmatic exercise program will be used for each participant needs based on physical therapy evaluation and goals. Each session will last approximately 60 minutes with five minutes warm up and five minutes cool down, three to five times per week for six weeks.

All patients will be charged for physical therapy services provided, as these services are standard of care, but there will be no charge for the LSQ use.

Upon completion of the trial, if LSQ results in outcomes improvements, the control group will receive six weeks of physical therapy using LSQ. All licensed therapists who participate in this research completed the Collaborative Institutional Training Initiative (CITI) training.

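### The investigator who decides eligibility also generates the randomisation file and treats both arms, so allocation is not assured to be concealed at enrolment

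*Combined protocol and SAP*

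**What the plan says.** All of this stands in the combined protocol and SAP, Methods, Study Sequence.

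- **Eligibility.** Investigator 1 conducts "screening (Appendix F) before they enroll the study to determine their eligibility".
- **Consent.** Mildly impaired patients who understand the study and are willing "will be asked to sign a consent form". For moderate impairment, both the patient and the legal representative are asked. The text does not say who obtains consent.
- **Sequence.** Allocation is 1:1 with "randomly permuted block sizes of 2 to 6 based on severity of cognitive impairment". "The randomization file will be generated by Investigator 1 (Physical therapist) not involved in the data collection process".
- **Custody.** The file is kept "with the results stored in a spreadsheet accessible only to the investigator responsible for" group assignment. That investigator is not named and will "not participate in any data collection".
- **Treatment.** "Investigator 1 will conduct all physical therapy sessions for the study patients".
- **Blinding.** Investigator 2, who rates the outcomes, is blinded. Participants are not.

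**The concern.** Concealment means that whoever decides on entry cannot know the next assignment until the patient is committed to the trial. Here the person who determines eligibility is the author of the list. If that person knows what comes next, who is entered, and when, can differ between arms.

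The primary outcome makes this relevant. The Pittsburgh scale in Appendix B rates effort and motivation as the therapist perceives them, which a screening physical therapist may be able to anticipate in a prospective patient. With 22 completers per group, a few selectively timed or declined entries could matter. Blinded rating and the intention-to-treat principle both act after enrolment, so neither can undo such selection.

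**Working it through.** **Step 1. Trace the roles.**

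| Task | Who |
|---|---|
| Determine eligibility | Investigator 1 |
| Obtain consent | Not stated |
| Generate the file | Investigator 1 |
| Hold the file | Investigator responsible for group assignment, not identified |
| Treat both arms | Investigator 1 |
| Rate outcomes | Investigator 2, blinded |

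The visible text describes only Investigators 1 and 2, and Investigator 2 is blinded. The holder is therefore Investigator 1 or someone unidentified. In either case the screener wrote the list. No independent generation, sealed envelope or release rule is described.

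**Step 2. Is there room for selection?** Some. Sampling is consecutive, and age, residence, language and the MMSE range of 10 to 23 are objective. The requirement of six weeks' attendance at physical therapy looks forward, however. Judging understanding and willingness takes discretion, and the timing of entry is open.

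**Step 3. How predictable is the next assignment?** The plan gives no figure to reproduce. Inputs from the documents are the 1:1 ratio, blocks of 2 to 6, severity (read here as a stratification factor), and 44 to 60 patients. Assumptions are block sizes 2, 4 and 6 equally likely (1:1 balance within a block needs even sizes) and tracking of past assignments within stratum.

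*List known to Investigator 1:* up to 100% of assignments are known.

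*List hidden, order of block sizes known.* In a block of size 2m, the expected number of assignments known with certainty is 2m/(m+1):

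- size 2: 1; size 4: 4/3; size 6: 3/2
- total 3.833 per 12 assignments, or 31.9%
- 0.319 × 44 = 14 patients; 0.319 × 60 = 19

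The expected number of correct guesses, always naming the under-represented arm and tossing a coin at a tie, is m + 2^(2m−1)/C(2m, m) − 1/2:

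- size 2: 1 + 2/2 − 0.5 = 1.5
- size 4: 2 + 8/6 − 0.5 = 2.833
- size 6: 3 + 32/20 − 0.5 = 4.1
- total 8.433 per 12, or 70.3%

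*List and order of block sizes both hidden.* Every block ends in balance, so the running imbalance within a stratum equals the imbalance within the current block. The same rule can be followed without knowing the block sizes. Simulation, which allows for an incomplete last block, gives:

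- correct guesses: 0.697 to 0.701 (0.697 × 44 = 31 patients; 0.699 × 60 = 42)
- known with certainty: 0.036 to 0.040 (0.038 × 44 = 1.7 patients; 0.038 × 60 = 2.3)
- other mixes of block sizes: 0.689 to 0.708 correct, 0.031 to 0.067 certain

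Hiding the list and the block order thus removes almost all certain knowledge but leaves average guessing at about 70%.

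**The case against.** **The holder may be a third person.** The group-assignment investigator could be someone else, and title and contact pages are not in the text reviewed. This stands as far as it goes: the 100% case is the worst reading, not an established fact. It does not restore concealment, because Investigator 1 would still have generated the list.

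**Investigator 1 is said to be outside data collection, and the rater is blinded.** True, but these protect measurement. Selection happens earlier.

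**The plan's order is screening, consent, assignment.** That is the order of the narrative. It is not a rule that keeps the assignment from the screener until the first two are recorded.

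**Timing is inferred.** No date is given for generating the list, and the Research Project Timeline gives only a data-collection window, May 2023 to September 2024. This stands in part. Staggered treatment is nevertheless likely. If sessions are one-to-one, 44 patients at three sessions of about 60 minutes would need 44 × 3 = 132 therapist hours a week, and one therapist delivers them all. Screening all at once before treatment begins is not excluded.

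**Selection is limited.** Consecutive sampling and mostly objective criteria narrow the room, and Appendix F assigns psychiatric history, diagnosis, MMSE range and referral to the front office. This stands and lowers the severity.

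**A stronger reading.** A reader might infer that selection will occur, that Investigator 1 certainly consults the list, or that the result will be biased in a given direction. The documents support none of these. They show that nothing stated prevents it.

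**Conclusion.** The point holds as an opportunity for selection at enrolment. The text gives one person eligibility, generation of the list and treatment in both arms, and it states no rule that withholds an assignment until eligibility and consent are recorded. The role conflict is written into the plan and is more than missing detail about custody.

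The size and direction of any bias cannot be derived, and no false-positive rate can be given. What can be computed is predictability: up to 100% of assignments known if Investigator 1 knows the list, about 4% known with certainty once the list and block order are hidden, and about 70% guessable even then. The last two figures rest on the assumed mix of block sizes and on tracking by stratum.

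A reader might infer that this is a fatal flaw. That goes too far: the effect is of unknown size, the sampling rules limit it, and the available remedy closes it only in part. It should be fixed, since no planned analysis can recover concealment after enrolment.

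**What to change.** In Study Sequence, replace the sentence that begins with "The randomization file will be generated by Investigator 1 (Physical therapist) not involved in the data collection process" and the sentence after it, in which the list holder will "not participate in any data collection", with:

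> The randomization list is generated in R and held by the investigator responsible for group assignment, who is neither Investigator 1 nor Investigator 2 and who does not screen, obtain consent, treat or collect data. The list, the seed and the order of block sizes are not accessible to Investigators 1 and 2. Each assignment is released to Investigator 1 only after that patient's eligibility and consent have been recorded.

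Both sentences must go. If the second were kept, it would attach to Investigator 1, although the same section says "Both investigators will enter their data using" a common platform. The sponsor must state which existing project role holds the list.

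Release is tied to eligibility and consent only, which is what concealment needs. The schedule of the first rating is left as it is.

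Add a limitation: Investigator 1 both screens and treats, and so sees past assignments, so about 70% of next assignments could still be guessed under the stated assumptions.

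The cost is a change of wording and a short hand-off per enrolment. Sample size, arms, outcomes and analysis are unchanged.

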Objectives: To evaluate the impact of LSQ on (1) participation in physical therapy using Pittsburg Rehabilitation Participation Scale; (2) quality of life using Quality of Life – Alzheimer’s Disease Scale (participant’s version); and (3) depression symptoms using Cornell Scale for Depression in Dementia (CSDD).

Methods: A consecutive sample of convenience of up to 60 patients with mild to moderate cognitive impairment with 44 (22 per group) completing the study will be recruited from a nursing home facility. Patients will be randomly allocated in two groups: (1) *Control group*, which will receive standard physical therapy care without LSQ use; and (2) *Experimental group*, where physical therapists will use the LSQ. Each patient’s family member will receive a LSQ to complete prior to the start of the intervention. Patients’ participation, quality of life and depression symptoms will be measured on day 1 and again after 3 weeks (mid-term), and 6 weeks of intervention. Quality of life and depression symptoms will also be measured 6 weeks following intervention. A licensed occupational therapist blinded to the participants’ group allocation will measure all three dependent variables

Statistical Analysis: Descriptive statistics including means, standard deviations, frequency counts, median, mode, variance and frequency counts will be used to assess sample demographics. The Rank Sum test will be used to assess differences in Pittsburg Rehabilitation Participation Scale between the intervention and control group. Spearman Rank correlations will be used to determine the strength of the correlation between Mini-Mental state examination, Pittsburg Rehabilitation Participation Scale and Quality of Life Alzheimer Disease.

Key words: Dementia, Life story questionnaire, Physical therapy, Participation, exercise

Financial Disclosure and Conflict of Interest: The investigators affirm that they have no financial affiliation (including research funding) or involvement with any

commercial organization that has a direct financial interest in any matter included in this manuscript.

NON-SCIENTIFIC ABSTRACT

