Example of LSQ usage: [name] has been diagnosed with dementia and scores 15 (Mild Cognitive Impairment) on MMSE scale. His family has completed LSQ and submitted it to the facility. All Peach Tree Place employees have access to LSQ to facilitate patient care. Patient's LSQ mentioned that patient loves coffee, enjoys playing cards and likes everything about cars. This patient is always excited to come to therapy when physical and occupational therapists (clinicians) mention drinking coffee together. Once patient arrives in therapy room, the clinician plays different card games with this patient in standing, to improve standing tolerance, also use balance board to challenge standing balance and to facilitate functional mobility. The clinician talks about cars, shows variety of car magazines while working on leg exercises. So, this clinician used various information from LSQ for this patient to motivate and improve therapy participation.

Outcome Assessment:

1. Pittsburgh rehabilitation participation scale (Appendix B) – to measure participant's participation in physical therapy
2. Quality of life in Alzheimer's disease – participant's version (Appendix C) – to access quality of life in dementia participants

3. Cornell scale for depression in dementia (Appendix D) – to access depression symptoms in dementia participants

Data Analysis

Descriptive statistics (means, medians, modes, standard deviations, frequency counts, minimum and maximum values) will be calculated using Excel version 2017 and SPSS version 20 (IBM Corp. Released 2011. IBM SPSS Statistics for Windows, Version 20.0. Armonk, NY: IBM Corp.) for the subjects' characteristics including age, gender, marital status, education, severity of cognitive impairment (MMSE) and living with family prior to admission to the dementia facility and the dependent and relationship variables.

Inferential statistics: the following statistics will be calculated using Jamovi version 1.6.

Research Questions 1-3: Because the data are ordinal (Pittsburg Rehabilitation Participation Scale, Quality of Life Alzheimer Disease, CSDD), the Mann-Whitney U test will be used to assess differences between the intervention and control group.

Research Question 4: Because the data are ordinal (MMSE, Pittsburg Rehabilitation Participation Scale) Spearman Rank correlations will be used to determine the strength of the correlation between MMSE and Pittsburg Rehabilitation Participation Scale.

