APPENDIX B: PITTSBURGH REHABILITATION PARTICIPATION SCALE

Patient name: _____

Date: _____

Instructions to therapist: for each therapy session, please circle one of each of the following to assess the patient’s participation (effort and motivation as perceived by you) in the therapy session.

Please rate as follows:

None: patient refused entire session, or did not participate in any exercises in session. (see Note below)

Poor: patient refused or did not participate in at least half of session. **Fair:** patient participated in most or all of exercises*, but did not show maximal effort or finish most exercises*, or required much encouragement to finish exercises*.

Good: patient participated in all exercises* with good effort and finished most but not all exercises* and passively followed directions (rather than actively taking interest in exercises* and future therapy).

Very good: patient participated in all exercises* with maximal effort and finished all exercises, but passively followed directions (rather than actively taking interest in exercises* and future therapy).

Excellent: patient participated in all exercises* with maximal effort, finished all exercises*, and actively took interest in exercises* and/or future therapy sessions.

Note: if patient was unable to attend therapy because of medical test, bed rest order, illness, or scheduling conflict, do not mark any score. Note: in cases of doubt, choose the lower rating, eg, “good” rather than “very good.”

Participation:

Session Number	Date	Therapist Initials	None	Poor	Fair	Good	Very good	Excellent
1 – prior to intervention			1	2	3	4	5	6
2 – 3-week			1	2	3	4	5	6
3 – 6-week			1	2	3	4	5	6
4 – 6-week following end intervention			1	2	3	4	5	6

* This version is specifically for physical therapists. For the occupational therapy form, “exercises” should be replaced by “activities”.

Source: <https://www.sralab.org/sites/default/files/2017-06/PITTSBURGH%20REHABILITATION%20PARTICIPATION%20SCALE.pdf>

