The Cornell Scale for Depression in Dementia (CSDD) was specifically developed to assess signs and symptoms of major depression in demented patients. Because some of these patients may give unreliable reports, the CSDD uses a comprehensive interviewing approach that derives information from the patient and the informant. Information is elicited through two semi-structured interviews; an interview of an informant and an interview of the patient. The interviewer should assign preliminary scores to each item of the scale on the basis of the informant's report in the "Informant" column. The next step is for the rater to interview the patient using the Cornell scale items as a guide. The interviews focus on depressive symptoms and signs occurring during the week preceding the interview. Many of the items during the patient interview can be filled after direct observation of the patient. If there are discrepancies in ratings from the informant and the patient interviews, the rater should re-interview both the informant and the patient with the goal to resolve the discrepancies. The final ratings of the CSDD items represent the rater's clinical impression rather than the responses of the informant or the patient. The CSDD takes approximately 20 minutes to administer.

Cornell Scale for Depression in Dementia

Participant Last Name: _____ First Name: _____

Date: __/__/202__

Scoring System:

- a = unable to evaluate 0
- = absent
- 1= mild or intermittent
- 2 = severe

Ratings should be based on symptoms and signs occurring during the week prior to interview. No score should be given if symptoms result from physical disability or illness.

A. Mood-Related Signs

- | | | | | |
|---|---|---|---|-------|
| 1. Anxiety | a | 0 | 1 | 2 |
| anxious expression, ruminations, worrying | | | | |
| 2. Sadness | a | 0 | 1 | 2 sad |
| expression, sad voice, tearfulness | | | | |
| 3. Lack of reactivity to pleasant events | a | 0 | 1 | 2 4. |
| Irritability | a | 0 | 1 | 2 |
| easily annoyed, short-tempered | | | | |

B. Behavioral Disturbance

- | | | | | |
|--|---|---|---|--------|
| 1. Agitation | a | 0 | 1 | 2 |
| restlessness, handwringing, hairpulling | | | | |
| 2. Retardation | a | 0 | 1 | 2 |
| slow movements, slow speech, slow reactions | | | | |
| 3. Multiple physical complaints | a | 0 | 1 | 2 |
| 4. Loss of interest | a | 0 | 1 | 2 less |
| involved in usual activities (score only if change occurred acutely, i.e.in less than 1 month) | | | | |

C. Physical Signs

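### The plan calls the outcome assessor blinded for all three outcomes, but the primary PRPS rating cannot be blinded as planned, and later CSDD ratings may not be

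*Combined protocol and SAP*

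**What the plan says.** The blinding claim appears twice. The abstract (Methods) states: "A licensed occupational therapist blinded to the participants’ group allocation will measure all three dependent variables". Methods, Study Sequence, repeats it for Investigator 2: "Investigator 2 measuring the dependent variables, however, will be blinded to the group assignment". The same section says that participants are not blinded.

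Investigator 1 generates the randomization file, is said to take no part in data collection, and delivers every physical therapy session. Investigator 2 collects PRPS, QOL-AD and CSDD at weeks 1, 3 and 6, and QOL-AD and CSDD again six weeks after the intervention.

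Appendix B addresses the PRPS form to the treating therapist, who scores each session. What is scored is "participation (effort and motivation as perceived by you) in the therapy session". Its anchors cover the share of exercises done, the effort shown, how much encouragement was needed, and active interest.

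The worked example of LSQ use shows what a session in the experimental arm can look like: "The clinician talks about cars, shows variety of car magazines while working on leg exercises".

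**The concern.** A PRPS score needs knowledge of what happened in the session, and the session is where the arms differ. Someone who has that knowledge is likely to know the arm, or to have it from someone who does. Participants and the treating therapist are unblinded, so assessor blinding is the only masking the trial claims, and its primary measurement lacks it.

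The planned PRPS difference is half a category on a six-point judgement scale. A modest tendency to score LSQ sessions higher could be mistaken for a treatment effect, and a report following the current text would call that result assessor-blinded. Because one person rates everything, knowledge of the arm gained from PRPS can also reach later CSDD ratings.

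**Working it through.** **1. Can PRPS be blinded under the assigned roles?** The documents do not say how Investigator 2 obtains the score. Two routes are evident:

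| Route | What follows | Blinded? |
|---|---|---|
| Investigator 2 watches the session | LSQ material is seen or heard in the experimental arm (Example of LSQ usage); control sessions run without it (Study Sequence) | Not reliably, from week 3 |
| Investigator 2 scores from Investigator 1's account | The information comes from the therapist who treats every patient and generated the randomization file. This also conflicts with the statement that this investigator takes no part in data collection | No |

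The plan describes no masked recording, separate PRPS rater, order of assessments, instruction not to disclose the arm, or check of blinding.

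**2. Which ratings are exposed?**

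- *PRPS:* weeks 3 and 6. Appendix B labels the first rating as taken before the intervention, whereas Study Sequence puts it on the first day of week 1. If Appendix B is followed, baseline is not exposed.
- *CSDD:* Appendix D makes the final item scores the rater's own clinical impression, drawn from "an interview of an informant and an interview of the patient". Ratings made after an LSQ session has been seen are exposed: week 6, follow-up, and week 3 if CSDD comes after the session.
- *QOL-AD:* in Appendix C the participant picks each response and the interviewer may not suggest one. Participants are already unblinded, so the assessor's knowledge adds little.

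**3. The plan's own figures.** Power Analysis gives a difference of 0.5 and an SD of 0.5, so d = 0.5 / 0.5 = 1, as stated. The stated 22 per group is not reproduced: d = 1, two-sided alpha 0.05 and power 0.80 need about 18 per group for a Mann-Whitney test on normal data. That is a separate matter; 22 per group is used below.

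**4. Sensitivity to rater bias.** Simulation with no true effect, 22 per arm, integer scores from 1 to 6 (rounded normal), and a two-sided Mann-Whitney test at 0.05 (the plan does not state sidedness). A share p of LSQ ratings is raised by one category. Mid-scale, the mean shift is p points: p = 25% gives 0.25, half the planned effect, and p = 50% gives 0.5, all of it.

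| Share raised | SD about 0.5, mid-scale | SD about 1.0, or scores near the ceiling of 6 |
|---|---|---|
| 0% | about 5% | about 5% |
| 10% | 7–9% | about 6% |
| 20% | 14–21% | 8–9% |
| 25% | 19–30% | 10–11% |
| 50% | 62–80% | 29–35% |

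Near the ceiling many raised scores are already at 6, so the effect is smaller. The last two figures in that column reach about 12% and 38% under some spreads.

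**5. Cross-check with a constant bias b added to every LSQ rating.** Noncentral t with Mann-Whitney efficiency 3/π = 0.955 and SD 0.5. Noncentrality = (b / 0.5) × √(22 × 0.955 / 2) = 3.24 × (b / 0.5).

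- b = 0.1: noncentrality 0.65, false-positive rate about 10%
- b = 0.2: 1.30, about 24%
- b = 0.25: 1.62, about 35%
- b = 0.5: 3.24, about 88%

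These exceed the simulated rates for the same mean shift because raising only a share of ratings also adds variance p(1 − p) to the LSQ arm, for example 0.25 × 0.75 = 0.19 on top of 0.25.

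**The case against.** The strongest reply is that observation is inferred. No section says that Investigator 2 watches a session, and the coffee, cards and car magazines come from one illustration, not a session specification. Control sessions are also individualised and include dual cognitive-motor tasks. Families in both arms complete an LSQ, so its existence does not reveal the arm. All of this stands: a reader might infer that the assessor certainly knows every patient's arm, and the documents support only that it is likely to be visible. But the other evident route, the treating therapist's account, is unblinded, so the blinding claim is unsupported either way.

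A reader might also infer that QOL-AD is compromised to the same degree. It is not, for the reasons in the working. Nor do the documents show that CSDD informants know the arm, since they are never identified.

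On size, a reader might conclude that a small rater tendency would produce a positive trial. The figures support only that it could: with 20% of ratings raised, about four in five null trials still come out negative, and with a larger SD or scores near the ceiling more than nine in ten do.

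Finally, relabelling the outcome does not lower the false-positive rate. That is correct, and the fix does not claim otherwise.

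**Conclusion.** The statement that all three outcomes are measured by a blinded assessor is wrong as written for PRPS, the primary outcome, and doubtful for CSDD once an LSQ session has been seen. This rests on the PRPS form, the assigned roles and the absence of any safeguard, not on the simulation.

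The size of any resulting bias is unknown. The documents give no rater-bias estimate and no mean PRPS, so the shares raised are assumptions. Over the range tried, the false-positive rate runs from barely above the nominal 5% (about 6% with 10% raised and an SD of about 1.0) to 62–80% (50% raised, SD about 0.5, mid-scale). At the plan's own SD and away from the ceiling, raising one rating in five gives roughly three to four times the nominal rate. The documents do not support saying that the arm is known in every case, that baseline is affected if taken as Appendix B labels it, or that QOL-AD is materially biased by the assessor.

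**What to change.** 1. In the abstract and Study Sequence, state how Investigator 2 obtains the PRPS score and withdraw the blinding claim for PRPS. Report and interpret the primary result as not assessor-blinded.
2. At each visit, complete CSDD and QOL-AD before the PRPS session is observed. Align the baseline timing in Study Sequence with the label in Appendix B, so that all baseline ratings and the week 3 CSDD and QOL-AD precede any sight of LSQ use. Describe the week 6 and follow-up CSDD as possibly unblinded.
3. Ask patients and CSDD informants not to mention the arm. Record the assessor's guess of the arm at each visit and report it with the results.

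The cost is protocol wording, a fixed order of assessments, a short instruction and one extra form item, with no added staff or sample. The primary outcome can no longer be described as assessor-blinded, and these steps do not remove bias in PRPS itself. The week 3 protection also depends on patients and informants not disclosing the arm. A separate CSDD rater who never sees sessions would extend protection to week 6 and follow-up, but needs another trained person.
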